4.1 Challenges in the Research Design

NEYAI could be described as multi-faceted in that it is *multi-programme* (11 different interventions), *multi-theme* (covering different aspects of child and parent well-being using a range of new and existing programmes), *multi-site* (each project works with different childcare centres), *multi-agency* (each project comprises a lead organisation and at least two other organisations), and *multi-level*

41 These outcomes include improved understanding each other's role, greater willingness to share information, reduction in duplication, better connection to local communities, etc. See Stratham, 2011; Barlow and Scott, 2010; CfBT Education Trust, 2010; Duggan and Corrigan, 2009; Oliver, Mooney and Stratham, 2010; Robinson, Atkinson and Downing, 2008.

42 See, for example, Inquiry Team in Roscommon Child Care Case, 2010; Lord Laming, 2003.

(initiative-level, thematic-level, project-level, learning community-level). Unlike a standard 'programme' evaluation – where programme is understood as a defined set of inputs and processes, often manualised, and delivered to either a population or specific target group – each of the 11 NEYAI projects has its own unique programme. In that sense, this could be described an evaluation of 11 programmes rather than one programme.

These complexities derive, at least in part, from the fact that, in its overall design, the objective of the initiative (which is to build a national evidence-base for policy and practice in the early years sector), is not fully aligned to the corresponding research requirements for producing a national scientific evidence-base. For example, projects were selected before an evaluation framework was put in place. A practical if understandable consequence of this design is that some projects have questioned why they are being funded to carry out a range of activities for all children in the 0-6 age range even though the evaluation, for reasons explained later in this section, can only evaluate a subset of those activities, albeit the subset which constitutes their most 'substantial and sustained' interventions. A further and potentially more serious consequence is that, while some projects are delivering programmes that are well-developed and already evidence-based, others appear to be at a much earlier stage in the cycle of programme design and development; when this is seen in the context of the relatively small effect sizes that well-developed manualised programmes can produce (see Appendix One), then the 'evaluation-readiness' of some projects might be questioned.

These challenges have been encountered in the course of preparing the research protocol, and to some extent have been resolved as much as they can be. There is also some reassurance, of a kind, that these difficulties are not unique to the evaluation of NEYAI since similar challenges were encountered in the evaluation of Springboard⁴³ in Ireland and Sure Start⁴⁴ in Britain. Nevertheless it is important that these challenges are recognised, not just as constraints on the evaluation but as part of the initial learning from the NEYAI about the need to ensure that, during the design stage,

43 'It is important to note that the diversity of interventions which constitute the Springboard programme pose a challenge for the evaluation since it is not possible to link outcomes to specific therapeutic inputs, given that the inputs vary widely in their approach and content. In other words, the design of the Springboard programme – which is similar to the design of many other family support programmes – limits the capacity of the evaluation to elucidate the mechanisms by which programme inputs are linked to programme outcomes' (McKeown, Haase and Pratschke, 2006; see also 2001).

44 'The great diversity among SSLPs [Sure Start Local Projects] posed a particular set of challenges for the National Evaluation in that there were not several hundred programmes delivering one well-defined intervention, but several hundred unique and multifaceted interventions operating in different places' (Melhuish and Hall, 2007:16). Similarly, Rutter has observed that 'there is no such thing as Sure Start in the sense of a defined programme with a definable intervention strategy (despite government implying the contrary). Instead, it constitutes a large 'family' of programmes that involve as much diversity as commonality.' (Rutter, 2006:138).

programmes which aim to produce an ‘a strong evidence-base’⁴⁵ must take into account the corresponding research requirements for producing a strong evidence-base.

4.2 Confirmatory Programme Evaluation

This research design is based on an approach that is sometimes referred to as confirmatory programme evaluation⁴⁶. This approach simultaneously assesses the impact of the programme and the pathways by which that impact may have come about. In order to do this, it is necessary to have a clear understanding of the theory which informs the programme – such as outlined in the logic model above - and to test the theory against the evidence. The principle steps in confirmatory programme evaluation are:

1. Specify programme theory and processes that are expected to affect outcomes.
2. Identify and measure outcomes and their timing over the short, intermediate, and long term.
3. Collect or obtain data on hypothesised mediators of the programme theory and key background variables necessary to identify programme impact.
4. Estimate main effects of programme participation for the total group and relevant subgroups, quantifying the temporality, size, gradient, specificity, consistency, and coherence of programme effects.
5. Where main effects are detected, test hypothesised causal mechanisms of the programme theory to account for estimated effects.
6. Interpret the pattern of findings to facilitate generalisation and knowledge transfer.
7. Identify formative uses of findings for programme improvement, including modifications to programme theory, programme implementation, and analysis of programme effects.

We now outline, based on this approach, how we answer the two core questions at the heart of this evaluation.

45 The Request for Tender For Evaluation of National Early Years Access Initiative emphasises the importance of ‘establishing a strong evidence-base to contribute to improvements in practice and ... policy’ (p.8).

46 According to Reynolds who first used the term, ‘Confirmatory evaluation is a theory-driven methodology for investigating the effects of social and educational programs. In a theory-driven impact evaluation, the explicit theory of the program is highlighted to establish an a priori model of how the program is expected to exert its influence. Causal uncertainty is reduced through an examination of the empirical pattern of findings against the expectations inherent in the program. ... Confirmatory evaluation attempts to strengthen causal inference through systematic investigation of the nature of the relationship between program participation and outcome. Special emphasis is given to testing causal mechanisms that are associated with program effectiveness. A major tenet of confirmatory program evaluation is that the plausibility of an estimated effect can be strengthened through systematic testing of causal mechanisms and other aspects of the program-outcome link, such as consistency and specificity of estimated effects. In the confirmatory evaluation approach, the theory of the program is used to document and interpret the pattern of findings to strengthen confidence in program-outcome links. ... Three key questions addressed are: Is program participation independently and consistently associated with key outcomes? Do the estimated effects vary by background characteristics, such as child and family attributes, or by program components? What are the processes or pathways through which participation leads to effectiveness in the short term and over time?’ (Reynolds, 2005:2401-2; see also 2004; 2002).

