This criterion suggests that, other things being equal, the larger the association between programme participation and outcome, the more likely the association represents a true effect. The requirement of 'other things being equal' draws attention to the possibility that the association may be due to the confounding effects of selection bias; for example, those who participate in the programme may be different from those who do not. Within the limitations of quasi-experimental design, these confounding effects are taken into account by controlling for all of the measured characteristics of programme participants.

3. Gradient (dosage-response)

This criterion implies that a causal inference is more justified if, other things being equal, there is a direct relationship between programme participation (such as the number of days or sessions attended, number of contact hours, number of years of participation) and the outcome. This criterion will be difficult to apply in this evaluation, particularly at initiative-level, because each project has a unique programme intervention with the result that dosages are not in equivalent units across projects. Moreover, within some projects, the concept of dosage is not clearly defined. Although gradient effects have been established in a number of early childhood evaluations⁵³, the dosage-response relationship may be direct inverse⁵⁴.

4. Specificity

This criterion refers to an association between a programme and an outcome which is quite specific to the theory underpinning the programme. For example, if NEYAI projects which focus on language or numeracy development have greater impact on cognitive outcomes than on social skills this would suggest, other things being equal, a causal link between those interventions and outcomes. Similarly, NEYAI projects which focus on enhancing the capacity of parents and which have a

51 See, for example, Reynolds, 2005.

52 See, for example, Bradford Hill, 1965.

53 Examples include studies of the Abecedarian Project (Campbell and Ramey, 1995), the Chicago Child-Parent Centers (Reynolds, 1994; Reynolds and Temple, 1998), and the Infant Health and Development Program (Ramey, et al., 1992).

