6.4 Template for Describing Each Project Intervention

Each NEYAI project is delivering a unique intervention. It is important therefore to have a clear description of that intervention for the evaluation since, where an intervention is shown to be effective, this will be valuable in helping to explain why this may have happened; additionally, it may also help to guide those who wish to replicate the intervention elsewhere. The interventions in the evaluation, as listed in Table 1 above, were selected to represent each project's most *substantial and sustained* intervention and, in that sense, could be regarded as the 'flag-ship' of each project, the impact of which will determine the success of their entire project.

A template will be prepared by the evaluation team to enable each project to prepare a detailed description of its intervention using the following headings:

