⁹⁷ This is an important assumption though seldom acknowledged due to the tendency to treat the 'personal' and the 'professional' as separate and unrelated domains of staff capacity. It is significant therefore that a recent review of the early childhood education drew attention to how child development is influenced by the capacities of all adults who interact with the child on a regular basis, both parents as well as childcare staff: '... although the call for more effective strategies to build parenting capacities is broadly accepted, the unmet, skill-building needs of service providers in these domains are acknowledged less frequently. Although many preschools are staffed by highly trained professionals, a large proportion of staff in early care and education programs have limited education, constrained work experience, and high rates of depression. Thus, large numbers of vulnerable children and highly stressed staff are engaged in dysregulated interactions on a daily basis that compromise early learning and undermine the ability to manage routine challenges and normative life stresses. Other indicators of unmet staff training needs include complaints about high rates of problematic child behaviors, increasing antipsychotic drug prescriptions for children as young as age 3, and large numbers of children being expelled from preschool programs. These signs of impending staff burnout underscore the need for expanded professional development activities to strengthen emotional health and executive function skills and self-regulation capacities of early childhood service providers.' (Shonkoff, 2011:983)

- ✓ Name of project and intervention
- ✓ Logic model of intervention and how it is expected to work in order to produce outcomes, including the mediating role of staff capacity
- ✓ History of intervention including evidence of its effectiveness in Ireland and elsewhere
- ✓ Target group of intervention (children, parents, staff) including measures used to recruit, retain and minimise drop-out
- ✓ Description of the intervention including method used to deliver the intervention such as individual-work or group-work, home-based or centre-based, etc.
- ✓ Duration of intervention broken down by number and length of each session including whether homework is part of the programme
- ✓ Resources needed to deliver the intervention such as manual, videos, handouts, etc.
- ✓ Staff recruitment, training and skills required to implement the intervention

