- ✓ Organisational structures to support intervention at childcare centre-level, project-level, inter-agency level
- ✓ Breakdown of the cost of undertaking the intervention, focusing on the additional cost over and above the existing 'overhead' cost of the centre and its staff
- ✓ Challenges encountered during implementation and how these were addressed.

The information provided by each project will form the basis for preparing case studies of effective interventions where the evaluation has already shown evidence of a significant impact on parent, child or staff outcomes. This information will also act as a 'manual' for other projects wishing to implement the intervention.

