9.2.6 Draw conclusions and implications from the evaluation. This is the final and, in some senses, the most important part of the evaluation since it cannot be assumed that 'results speak for themselves'; results can be over-interpreted, under-interpreted or simply misinterpreted and this can undermine the entire evaluation. We have already underlined the centrality of interpretation in the overall research design above (Section 4.4) and the careful work that is required to translate research findings – specifically statistically-significant associations between variables – into a plausible understanding of how those variables may relate to each other as cause and consequence. Equally, it is important to acknowledge that while variables may co-vary, a causal sequence cannot always be established either because the temporal 'before-and-after' sequence is unknown, or the mechanism and 'agency' connecting them is not understood. Within these limitations, the evaluation will use our analysis and interpretation of the evidence to draw out the implications for action since that is the *raison d'être* of the entire initiative. These implications may well confirm what is already known about the factors associated with positive outcomes for children and their parents but this finding, in itself, may provide the motivation that is sometimes missing in order to link knowledge to action. Equally, the implications may draw attention to variables that have no measurable impact, directly or indirectly, on outcomes and this may also be useful, particularly where existing policies and practices are based on assumptions that give undue importance to these variables.

105 Request for Tender For Evaluation of National Early Years Access Initiative, 2011:9.

10. Outputs from the Evaluation

The outputs of the evaluation, including a timetable for their delivery, are summarised in Table 4.

Table 4 Delivery Dates for Core Outputs of Evaluation

Core Outputs of Evaluation	2011	2012	2013	2014
	Final Delivery Dates			
Research Protocol	Oct			
Baseline surveys of child, parent and staff		Oct		
Data Extraction on area-characteristics of projects		Jan		
Data Extraction from Growing Up in Ireland database		Dec		
Interim Report			Mar	
Follow-up surveys of child, parent and staff			Jun	
Description of project interventions			May	
Case studies of individual service models			Dec	
Monitoring and evaluation of learning community	ongoing			
Progress Reports and Updates	ongoing			

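### Project logic models are not due until May 2013, so for six of the 11 projects a theory-consistent pattern carries less evidential weight under the specificity and coherence criteria

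*Protocol*

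**What the plan says.** - Section 4.2 lists the steps of confirmatory programme evaluation, the first being to "Specify programme theory and processes that are expected to affect outcomes". It points to the logic model of Section 3 as an example of such theory. Footnote 46 describes the approach as one in which "the explicit theory of the program is highlighted to establish an a priori model of how the program is expected to exert its influence".
- Section 4.1 stresses that "each of the 11 NEYAI projects has its own unique programme" and that this could be seen as 11 evaluations.
- Section 4.4 sets out criteria for causal interpretation. Under specificity, the association should be "quite specific to the theory underpinning the programme"; the examples are language or numeracy projects and parent-capacity projects. Coherence asks whether the proposed mechanism is plausible given existing knowledge and the programme's theory, using a pathway model supplemented by case studies.
- Section 6.4 is where a project's own theory is requested. "A template will be prepared by the evaluation team to enable each project to prepare a detailed description of its intervention", and one heading is "Logic model of intervention and how it is expected to work in order to produce outcomes, including the mediating role of staff capacity". Another heading in the same template is "Challenges encountered during implementation and how these were addressed".
- Table 4 (Section 10) lists "Description of project interventions" with a final delivery date of May in the 2013 column.
- Section 7 closes baseline at the end of October 2012 and follow-up at the end of June 2013. Table 4 dates the Interim Report March 2013.

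**The concern.** Specificity and coherence strengthen a causal reading only if they could also have failed. That requires the expected outcome and pathway to be on record before anyone can see how things are going. For some projects the protocol gives no specific expectation, and the document that would give it is due almost at the end of data collection.

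The project side is well placed to know how its children are doing by then. Coordinators compile the intervention description (Appendix Two, item 13), and centre staff rate the children at baseline and follow-up (Section 6.1). Section 6.4 then uses the descriptions for case studies only where an impact has been shown. A theory written late and consulted mainly for successes can count for a project but hardly against it. At stake is the project-level part of core question (ii): in which projects, and through which type of intervention, an impact arises.

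**Working it through.** No sample-size arithmetic applies. The check is a comparison of dates and a reading of Table 1 against the criteria.

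**1. The date.** The columns of Table 4 are 2011 to 2014. The May entry for the project descriptions sits in the same column as the Interim Report (March) and the follow-up surveys (June). The text independently places those in early 2013 (Section 9) and June 2013 (Section 7), so the entry is May 2013.

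**2. Distance from the other milestones.**

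| Milestone | Date | Distance to May 2013 |
|---|---|---|
| Baseline closes | October 2012 | 7 months before |
| Interim Report | March 2013 | 2 months before |
| Follow-up closes | June 2013 | 1 month after |

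The window between the outer deadlines is October 2012 to June 2013, or 8 months. By May 2013, 7/8 = 87.5% of it has passed. Section 7 wants follow-up as soon as possible after each intervention ends, so a project that finishes before June could have completed its intervention, and even its follow-up ratings, before its logic model is due. May 2013 is an outer limit: earlier delivery is allowed, but nothing in the protocol requires it.

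**3. What Table 1 fixes in advance.**

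| Projects | What Table 1 gives | Specific outcome area? |
|---|---|---|
| BC, CK, RO | Child language, with parent support for it | Yes |
| DD | Child numeracy, with parent support for it | Yes |
| FL | Two named parenting courses | Yes (parenting, read from the courses) |
| CC | Named programmes; child and parent outcomes in general; outreach | No |
| CN | Mentoring; child and parent outcomes in general | No |
| DL, LD | Training and mentoring; child outcomes in general | No |
| LK | Síolta standards; outreach to children and parents | No |
| TT | Delivery of a named training manual | No (activity only) |

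Count: 3 + 1 + 1 = 5 with a specific area, and 11 − 5 = 6 without.

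**4. Whether Figure 1 closes the gap.** It states the initiative's inputs, pathways and outcomes in advance. It does not say which outcome a given project should move, and the end of Section 3 leaves open how its elements connect in practice. It therefore supports an initiative-level test, but not a specificity judgement on, say, CN or LD.

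**5. Where project theory enters.** It is needed for the specificity and coherence criteria (Section 4.4) and for the detailed account of interventions behind positive impacts (Section 9.2.4). It does not enter the estimation of net impact (Sections 4.5 and 9.2.2) or the pathway models (Section 9.2.3).

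**The case against.** A reader might infer that step 1 of Section 4.2 is itself postponed to May 2013, so that the evaluation is not confirmatory at all. The protocol does not support that. Section 4.2 ties the theory to the logic model already presented, Section 4.4 tests the hypotheses of that model, and Section 9.2.3 tests its pathways. All of these refer to Figure 1.

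A reader might also infer an inflated false-positive rate, as if each project could pick its best-looking developmental domain and have that alone tested. No such test is planned. Section 4.5 assesses every project on every set of outcomes whatever target is named, Section 9.1.2 builds multivariate latent outcomes, and Section 9.2.3 takes a single outcome for each of children, parents and staff. No error rate should be attached to this point.

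Other objections have some force:

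- The template is meant to explain and replicate interventions already shown to work, and its cost and implementation headings cannot be completed early. This stands, and is a reason to split it rather than move all of it.
- Figure 1 draws on the projects' work plans, so project-level documents exist. They do, but the protocol does not make them the reference for specificity or coherence.
- A broad staff-training project may have a broad theory rather than a missing one. That is fair for some of the six. A broad theory still gives specificity little to test.
- In May 2013 projects would not have estimated net impacts, and the by-project layout of Table 2 is only a possible format. Both are true. Baseline results and delivery experience remain possible influences.
- Locking target outcomes may be left to a statistical analysis plan, which is not shown. The delivery date and the template are nevertheless fixed in the protocol.

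**Conclusion.** The point holds at project level only. Initiative-level theory is stated in advance and is what the models test; core question (i) is untouched and no planned test changes. For six of 11 projects, no specific outcome area is on record until a document due 7 months after baseline closes and 1 month before follow-up closes. A finding that such a project behaved as its theory predicts therefore carries less evidential weight than Section 4.4 would give it. The loss is one of interpretation and cannot be put as an error rate.

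This rests on reading Table 1 as the protocol's only advance statement of project targets, and on no earlier lodged version being required elsewhere. If projects have already lodged dated logic models, the point reduces to citing them. It is a cheap improvement rather than a flaw that threatens the main result.

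**What to change.** Split the Section 6.4 template. Each project completes the logic-model heading, naming its target outcomes and pathways from among those measured by the Child, Parent and Staff Questionnaires, and lodges it, dated, with the evaluation team before its own baseline and no later than October 2012. The description, cost and implementation headings stay at May 2013. Table 4 gains a row for the lodged section. Sections 4.4 and 9.2.4 should state that project-level specificity and coherence are judged against the lodged version, including where the pattern fails to match, and that later additions are labelled post hoc.

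The cost is 11 short forms completed earlier and one extra line in Table 4, with no new data or participants. The drawback falls on projects still developing their programmes, which Section 4.1 acknowledges exist: they may have to revise their theory, and the revision would carry the post hoc label.
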